9.1 Definition Serious Events

A **serious event (SE)** according to HFV Art. 21 is any unfavorable event for which a causal relationship the collection of health related personal data cannot be ruled out, and which:

- Requires hospitalization or prolongation of an inpatients' hospitalization,
- results in persistent or significant disability or incapacity, or is life-threatening or results in death

If a serious event occurs the research project must to be set on hold.

9.2 Assessment and Documentation of SEs

The assessment by the project leader regarding the causal relationship of the event to the project-specific measure is done according to the following definitions:

Unrelated	
• The event started in no temporal relationship to the project-specific measures applied and• The event can be definitely explained by underlying diseases or other situations.
Related	
• The event started in plausible time relationship to the project-specific measures applied and• The event cannot be definitely explained by underlying diseases or other situations.

All SEs are to be documented in the subjects' file and on the SE report form.

9.3 Reporting of SEs

SEs will be treated according to the Human Research Ordinance (HFV Art. 21). First, the project leader will report any occurring SE to the responsible ethics committee within 7 days. He will also submit a report which evaluates the relationship between the event reported and the methods of collecting health related personal data or sampling of biological material within that project, furthermore proposals how to proceed with the project.

9.4 Reporting of Safety and Protective Measures

The project leader shall notify any immediate safety and protective measures, which have to be taken during the conduct of the research project, the ethics committee within 7 days according to the HFV Art. 20. In addition, the project leader explains the circumstances which necessitated the safety and protective measures.

10 Data - und Quality Management

The principal investigator and the whole study team affirm to uphold the principles of the participant's right to privacy and that they shall comply with applicable privacy laws. Especially, anonymity of the participants will be guaranteed when presenting the data at scientific meetings or publishing them in scientific journals. Individual subject medical information obtained as a result of this study is considered confidential and disclosure to third parties is prohibited. Subject confidentiality will be further ensured by utilising subject identification code numbers to correspond to treatment data in the computer files. For data verification purposes, authorised representatives of the Sponsor (-Investigator) or an ethics committee may require direct access to parts of the medical records relevant to the study, including participants' medical history.

A good-clinical-practice educated member of the study team is responsible for proper, coded and correct data management. All patient related electronic data is stored coded in a password-protected folder on our institution server. Only dedicated study personnel have access. All physical data and patient informed consent is stored in a locked folder at our institution's secretariat. Data storage is only performed in coded form for peer-review. For further informations also see Chapter 8.

11 Statistical Plan

11.1 Determination of Sample Size

Within a study period of 6 to 12 months, all elective and emergency patients scheduled for a Rapid Sequence Induction (RSI) will be included in this study. In 2019, a total of 2'718 general anaesthesias with Rapid Sequence Inductions (RSI) were undertaken at our institution. 275 thereof were children < 18 years of age. Further, 204 Rapid Sequence Inductions were performed in life threatening situations (category: Notfall <1h, vital, sofortiger Eingriff notwendig by the Swiss Society for Anaesthesiology and Resuscitation, A-QUA) where a delay is medically and ethically not acceptable. Further, we estimate that a number of 1000 patients per annum have one or more aspiration risk factors, receiving an advanced laryngeal mask or a regional anaesthesia. In conclusion, we aim to include at least 1500 up to 3200 patients in a one year recruitment period. On basis of the publication of Arzola et al.³⁶ individual differences in sonography performance can already be detected after 30 to 40 examinations. Although our residents will already have performed at least as many examinations before first patient inclusion, we postulate, that a similar number of patients per capita will be needed to investigate interindividual performance. Given an estimated number of 30 residents and 20 attendings participating, we aim to include 1500 - 2000 patients.

11.2 Statistical Methods

Primary Endpoint:

- Correlation of sonographic estimated gastric volume with volume aspirated through a naso- or orogastric tube.

Secondary Endpoints:

- Performance over time (improvement of examination technique, critical number of examinations).
- Association of performance with experience, residents vs. attendings.
- Number of patients classified as empty -> possible implications for management and induction.
- Number of patients with full stomach -> possible implications for management and induction.
- Time used for examinations, time used with growing experience.
- estimated aspiration risk vs. sonographic gastric volume.
- Total number of pulmonary aspirations.

Collected Variables:

- Patient Demographic: Age, sex, gender, height, weight, BMI, ASA Classification, patient history, concomitant medication, concomitant disease, intervention performed, anaesthetic risk class of the intervention, surgical department of the intervention, urgency of the intervention.
- Sonographer Demographic: education level, years of anaesthesiologic experience, years of sonographic experience.
- RSI Indication.
- Last meal/ drink before surgery.
- Subjective estimated aspiration risk (graded by the responsible anaesthetist).
- Sonography quality, reasons for poor quality.

- Sonographic quality of gastric content.
- Sonographic quantity of gastric content.
- Time for examination.
- Effective quantity of gastric content.
- Theoretical change in anaesthesiologic management.
- Reason for not performing gastric sonography.

Analysis:

- Demographic Analysis.
- Institution overall success analysis.
- Interpersonal success analysis with logistic regression and cumulative sum learning curves.
- Analysis of possible changes in anaesthesiologic management.

12 Ethics

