GCP Statement:	
This study will be conducted in compliance with the study protocol, the current version of the Declaration of Helsinki, the ICH-GCP directive, the HFG and HFV as well as all other relevant national legal and regulatory requirements.

Study Schedule

	Expert and Resident Training in Sonography (11/2020 – 02/2021)	Screening (01/2021 – 12/2021) Prior to arrival at OR suite	Day of Surgery (01/2021 – 12/2021) = Day 1
Expert (study core group, faculties) Training	√		
Anaesthesia resident Training	√		
Training Participants Demographic and Experience Data	√		
Participant Information and Informed Consent		√	
Inclusion- and Exclusion Criteria		√	
Demographic Data		√	
Medical History / Concomitant Diseases / Concomitant Medication		√	
Sonography and Data Collection			√
Gastric Volume direct measurement			√
Serious Events			√

Table of Contents		Page
1	Abbreviations	8
2	Project Personal and Administration.....	9
3	Introduction	10
3.1	Background and Project Purpose	10
3.2	Categorisation	11
4	Project Objectives	12
4.1	Project Objectives	12
4.2	Project Outcomes.....	12
5	Project Description	13
5.1	Design	13
5.2	Number of Project Participants	13
5.3	Project Schedule	13
5.4	Risk-benefit considerations.....	13
6	Eligibility of the Project Site.....	14
7	Recruitment	15
7.1	Inclusion Criteria	15
7.2	Exclusion Criteria	16
7.3	Premature Withdrawal Criteria.....	16
8	Project Measures	17
8.1	Measures/procedures to collect health related personal data	17
9	Safety	19
9.1	Definition Serious Events.....	19
9.2	Assessment and Documentation of SEs	19
9.3	Reporting of SEs	19
9.4	Reporting of Safety and Protective Measures	20
10	Data - und Quality Management.....	21
11	Statistical Plan.....	22
11.1	Determination of Sample Size	22
11.2	Statistical Methods	22
12	Ethics	24
12.1	Independent Ethics Committee	24
12.2	Ethical Conduct of the Project.....	24
12.3	Participant Information and Informed Consent	24
13	Confidentiality and Data Protection.....	25
14	Funding and Support.....	25
15	Compensation	25
16	Insurance	25
17	Publication Policy	26
18	Signatures	27
19	References.....	28

1 Abbreviations

HFG	Humanforschungsgesetz
HFV	Humanforschungsverordnung (Ordinance on human research with exception of clinical trials/HRO)
HRO	Human Research Ordinance
ICH	International Conference on Harmonization
SE	Serious Event
RSI	Rapid Sequence Induction
POCUS	Point-of-care ultrasound
CSA	Cross sectional area
SGAR	Swiss Society for Anaesthesiology and Resuscitation

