8.1 Measures/procedures to collect health related personal data

At Kantospital Winterthur, a mid-size Swiss teaching hospital all residents and attending anaesthesiologists will receive a structured training in a period of 1 to 8 weeks before inclusion of the first patient. All participating staff will give written informed consent to participate in the study.

To achieve a 90% success rate in correctly recognizing gastric content quality in healthy volunteers, Arzola et al.³⁶ postulated an average number of 24 sonographic examinations to be performed. Based on this and further scientific studies we designed a structured training for all residents and fellows. Primarily, at least 120 minutes of self-study is mandatory for all participants, consisting of scientific background literature, a step for step guide and educational videos. This is followed by a hands-on course, split into a 30 minute lecture and theoretic background introduction and 120 minutes supervised practical training on healthy volunteers. Group sizes per ultrasound machine and tutor/expert will range from 2 to 3 participants. First training objective is a successful differentiation of gastric content into empty, fluid, solid or mixed. An empty stomach seems the hardest quality to sonographically visualise,³⁶ therefore a special effort will be made on identifying this quality. The next objective is the identification and localization of the antral cross-sectional area in a supine and right lateral decubitus (RLD) position in the case that fluid gastric content is present. Every participant will perform at least 20 examinations during this hands-on course with a direct expert feedback.

Further, all participants will continue to train their sonographic skills on healthy volunteers and team members at our institution. Before including the first patient all the examiners will be tested by a tutor/expert and received their approval. In the first month of recruitment, new sonographers will be supervised by our tutor/expert team whenever possible. Individual feedback and support if needed should be available any time.

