Tutors/experts are all expert sonographers on different modalities. They will receive a preceding 240 minutes training, consisting of a 60 minutes theoretic introduction and a 60 minutes course by a radiologist and abdominal sonography expert, certified by the Swiss Society for Sonography. The remaining time will consist of individual exercise on healthy volunteers and at least 10 trial sonographies with gastric volume calculation under supervision of another member of the tutor group.

Our study will be performed mainly in the induction rooms of our operating unit and occasionally inside the operating theatre. Standard care will be given to every patient at the usual location, with our usual equipment (anaesthetic machine, monitoring, medication and airway devices and so on) and by our usual anaesthesiologic team members. Sonographic examination and determination of the gastric content will be executed on one of our standard ultrasound machines (Venue and LOQIC e from GE-Healthcare®) with a curved array low frequency (2-10 Hz) abdominal probe or our portable ultrasound devices (IQ+ from Butterfly Network Inc.®).

Before performing the sonographic examination, the responsible anaesthesiologist will be asked to rate the estimated risk of pulmonary aspiration, based on personal impression, patient history and clinical finding. All anaesthetists are advised to perform the examination only if they could guarantee privacy before they expose patient abdomen for the examination. Primarily, a qualitative assessment of the gastric content should be performed in supine and right-lateral decubitus (RLD) position. In low volume states a right-lateral decubitus position (RLD) has the advantage of a gravitational shift to the antrum. That is why we plan to perform the examination in both positions. If RLD position is not possible due to patient factors a half sitting position can be tried. Gastric content will be classified into empty, fluid, solid or mixed. Examiners will be asked to classify sonographic conditions into poor, medium or good and provide a reason in case of limited conditions. If fluid gastric content is detected an estimation of the quantity should be performed as follows.

After identification, CSA will be measured and gastric content is estimated by implementation of the formula described by Perlas et al: ^{20, 28}

$$\text{Gastric Volume (ml)} = 27.0 + 14.6 \times \text{right-lateral CSA (cm}^2\text{)} - 1.28 \times \text{age (years)}.$$

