This model is based on gastroscopic fluid assessment and highly validated by several publications. ²⁸

After placement of the routine naso- or orogastric tube, which is a standard procedure for both RSIs and advanced laryngeal masks at our institution - we compare the calculated and effective suctioned volume of the gastric content and analyse the difference and quality of the sonographic measurement. In some patients a gastric tube is contraindicated or not possible to place correctly. In this case an exclusion of the study is mandatory according to our exclusion criteria. Patients planned for an intervention in a regional anaesthesia will not receive a gastric tube.

In exceptional cases the responsible anaesthesiologist is allowed to upgrade patients from an advanced laryngeal mask to an RSI after ultrasound performance to ensure patient safety. Downgrading from RSI to advanced laryngeal masks on base of the ultrasound results is not allowed.

All data concerning the sonography will be noted in a password protected Excel sheet only available to institute members by the responsible anaesthesiologist performing the examination. Background patient data including demographic data are collected during the structured preoperative anaesthesiologic assessment according to in house standard procedures and data management. Data will be coded and condensed in a password-protected Excel File, only accessible to study personnel. A patient identification log will be kept in a locked archive for data verification processes only. To guarantee seamless traceability we will create a immutable PDF file after all relevant changes or at least once per month and store it in a separate study folder only accessible to study personnel. An additional hard copy will be created and printed once per month and stored in a locker in our administrative office.

9 Safety

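### The reference measurement records only the aspirate's volume, so fluid, solid and mixed calls cannot be verified and empty calls only indirectly

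*Protocol*

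**What the plan says.** Section 11.2 lists two ultrasound variables, "Sonographic quality of gastric content" and "Sonographic quantity of gastric content". The only counterpart on the reference side is "Effective quantity of gastric content". The synopsis (Statistical Considerations) repeats the same three items. The study schedule table has a single row for the reference, "Gastric Volume direct measurement". On what happens once the tube is in place, section 8.1 says: "we compare the calculated and effective suctioned volume of the gastric content and analyse the difference and quality of the sonographic measurement". Nothing in the protocol asks for the character of the suctioned material.

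The content class nevertheless carries weight:

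- **Training (8.1):** "First training objective is a successful differentiation of gastric content into empty, fluid, solid or mixed". The course is built around a cited benchmark of 90% success in recognising content type in healthy volunteers.
- **Examination (8.1):** "Gastric content will be classified into empty, fluid, solid or mixed", and then "If fluid gastric content is detected an estimation of the quantity should be performed as follows". Only a fluid call leads to a volume.
- **Objective (4.1):** the training is to be validated by setting the sonographic estimate against directly measured gastric content.
- **Endpoints (4.2):** the number of patients classified as empty rests on the class. The quality standard for the learning curve is congruence above 80%, for volume in fluids.

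**The concern.** The study sets out to validate a training whose first skill is recognising the type of content, but the tube provides a recorded reference for amount only. Two kinds of examiner error then become hard to tell apart. One is recognising the wrong content; the other is measuring the antral area badly. They call for different teaching, and the protocol's success analyses and learning curves are meant to guide teaching.

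The primary comparison is exposed as well. A false fluid call adds a pair whose disagreement has nothing to do with measurement. A fluid stomach called solid or mixed contributes no pair, so that error is not counted and the remaining set is selected by the examiner's own call. An analysis plan written later can define how to handle such cases, but it cannot recover a feature of the aspirate that nobody recorded.

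**Working it through.** **1. The plan's own figure.** Section 11.1 takes 30 residents and 20 attendings at 30 to 40 examinations each: (30 + 20) × 30 = 1500 and (30 + 20) × 40 = 2000. This reproduces the stated 1500 to 2000. The 30 to 40 comes from the cited learning-curve study (reference 36), whose title says it concerns qualitative assessment. The per-examiner number is thus borrowed from learning to recognise content type, while the protocol's own standard (4.2) is volume congruence in fluids.

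**2. What each call can be checked against in a tube patient.**

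| Sonographic call | Formula volume (8.1)? | Recorded reference | What an error looks like |
|---|---|---|---|
| Fluid | Yes | Suctioned volume | Solid or mixed content called fluid appears as volume error |
| Solid or mixed | No | Suctioned volume, with no estimate to pair | Missed fluid leaves the comparison |
| Empty | No; scoring as 0 ml is not stated | Suctioned volume, no cut-off given | A large aspirate exposes the error; a small one may still mean solids |

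**3. Size of one false fluid call.** The section 8.1 formula is volume = 27.0 + 14.6 × area − 1.28 × age. At age 50 the age term is 64.0, so:

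- area 5 cm²: 27.0 + 73.0 − 64.0 = 36.0 ml
- area 8 cm²: 27.0 + 116.8 − 64.0 = 79.8 ml
- area 10 cm²: 27.0 + 146.0 − 64.0 = 109.0 ml
- area 15 cm²: 27.0 + 219.0 − 64.0 = 182.0 ml

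If the stomach holds solids and little comes up the tube, almost the whole figure enters as error.

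**4. Illustration of the effect on the correlation.** All inputs here are assumptions; none comes from the protocol. True fluid volume is gamma distributed with shape 2 and scale 40 (mean 80 ml, variance 3200). Measurement SD is 25 ml. A share m of fluid calls is really solid, has the same distribution of formula volumes, and yields 0 to 10 ml uniformly (mean 5 ml). The mean bias is then m × (80 − 5). Simulation with 200,000 pairs gave:

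| Share m of fluid calls misread | Correlation | Mean bias (ml) |
|---|---|---|
| 0% | 0.91 | 0.0 |
| 5% | 0.85 | 3.8 |
| 10% | 0.80 | 7.5 |
| 20% | 0.70 | 15.1 |

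The formula gives 3.75, 7.5 and 15 ml for the last three rows, which agrees. The table shows direction only. With the variables now listed, such a fall could not be distinguished from poor measurement of the antral area.

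**The case against.** Four arguments deserve weight.

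- **Class accuracy is not an endpoint.** The primary endpoint is a volume correlation, the quality standard is volume congruence in fluids, and the count of patients classified as empty can be reported as defined. This stands: the protocol does not promise a diagnostic-accuracy result for content type. It does not answer the mixing of recognition and measurement error inside the primary comparison.
- **The qualitative skill is checked elsewhere.** Section 8.1 requires at least 20 examinations with expert feedback, a test and approval by a tutor before the first patient, and supervision in the first month where possible. This lowers the urgency, but it gives no recorded check of calls in study patients.
- **A variable list is not a data sheet.** The lists also omit pulmonary aspiration events, although these are a secondary endpoint, and the data sheet is not shown. An appearance field could exist there. The schedule and section 8.1 also speak only of volume, so the protocol as written does not provide for one.
- **The remedy is partial.** Solids may not pass the tube, so a clear aspirate proves little. This stands and has to be stated.

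A reader might infer that the whole four-way call lacks any reference. The documents do not support that, because suctioned volume is a partial check on empty against fluid. A reader might also infer that every misread becomes volume error. Under section 8.1 only false fluid calls do so.

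**Conclusion.** The gap is real and limited. In tube patients, calls of fluid, solid or mixed cannot be verified as to type, and calls of empty only indirectly. False fluid calls enter the primary comparison as volume error, and fluid called solid or mixed leaves it. This follows from the collected variables as listed and assumes that the unseen data sheet holds nothing more.

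No count of affected calls can be given. It is tempting to apply a guessed share of solid or mixed scans to the planned 1500 to 2000 patients. The protocol states no such share, and eligible regional-anaesthesia patients receive no tube, so the relevant denominator is smaller by an unstated number. The correlations shown above are likewise no estimate of this study's result. The point is a cheap improvement that is best made before enrolment; it does not invalidate the design.

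**What to change.** Add one item to the variable lists in the synopsis and section 11.2: appearance of the aspirate (none / fluid / particulate or mixed), entered at the suction already performed. Then:

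1. Cross-tabulate it with the sonographic class in tube patients.
2. Count an empty or fluid call with a particulate or mixed aspirate as misclassified.
3. Repeat the primary volume comparison without those cases as a sensitivity analysis.
4. Report the suctioned volume among calls of solid or mixed, so that possible missed fluid is visible.

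The cost is one tick-box, one table and one repeat analysis, with no added procedure, staff or patient burden. The protocol should state the limits. The check is one-sided, because solids may not pass the tube. It finds only some false empty and false fluid calls, cannot refute a solid or mixed call, and does not cover regional-anaesthesia patients.

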4.2 Project Outcomes

Primary Endpoint:

- Correlation of sonographic estimated gastric volume with volume aspirated through a naso- or oro-gastric tube, that was placed by routine.

Secondary Endpoints:

- Performance over time, improvement of examination technique, critical number of examinations to achieve a high quality standard (>80% congruence for estimated and aspirated gastric volume in fluids).
- Association of performance with experience, residents vs. attendings.
- Number of patients classified as empty -> possible implications for management and induction.
- Number of patients with full stomach -> possible implications for management and induction.
- Time used for examinations, time used with growing experience.
- Estimated aspiration risk vs. sonographic gastric volume.
- Total number of pulmonary aspirations.

5 Project Description

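### The only methods named for examiner performance use success/failure, although a volume error in ml is available for every fluid scan with a gastric tube

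*Protocol*

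**What the plan says.** Section 11.2 lists as a secondary endpoint "Association of performance with experience, residents vs. attendings". The only methods it names for examiner performance are "Interpersonal success analysis with logistic regression and cumulative sum learning curves". The primary endpoint stays on the ml scale, as a correlation across patients, but it does not address grade or experience.

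The data behind these analyses are described in section 8.1. An estimated volume in ml is calculated from antral area and age, but only for fluid content: "If fluid gastric content is detected an estimation of the quantity should be performed as follows". Suctioned volume comes from the routine gastric tube, which regional-anaesthesia patients do not receive. The same section says "we compare the calculated and effective suctioned volume of the gastric content and analyse the difference and quality of the sonographic measurement".

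The one performance standard stated for the study is in section 4.2: ">80% congruence for estimated and aspirated gastric volume in fluids". The protocol does not say what makes a single scan a success.

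**The concern.** A success/failure result counts a miss just outside the limit the same as a gross miss. It does not show whether an examiner over- or underestimates, and it makes the answer depend on where the limit lies.

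This matters because section 11.1 sizes the study on differences between examiners. Not every included patient contributes a volume comparison: the content must be fluid and a tube must be placed. The usable scans per examiner will therefore be fewer than the 30 to 40 planned, so losing information from each one has a cost. Section 8.1 intends to analyse the volume difference, but section 11.2 provides no matching method for the questions on grade and experience.

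**Working it through.** **The plan's own figure.** 30 residents + 20 attendings = 50 examiners. 50 x 30 = 1500 and 50 x 40 = 2000, which reproduces the stated 1500-2000. The protocol gives no success rate, standard deviation or intraclass correlation (ICC). Everything below therefore uses assumed values and normally distributed errors.

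**1. Loss per scan, one-sided cut, shift in mean.** Information kept = phi(z_p)^2 / [p(1-p)], where p is the success rate. At p = 0.8: z = 0.8416, phi = 0.280, and 0.280^2 / 0.16 = 0.490.

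**2. Loss per scan, two-sided limit (|error| < c), difference in spread.** Information kept = [2c phi(c)]^2 / [2p(1-p)], with c = z at (1+p)/2. At p = 0.8: c = 1.2816, phi(c) = 0.1755, and (0.4498)^2 / 0.32 = 0.632.

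| Success rate | One-sided: kept / lost | Two-sided: kept / lost |
|---|---|---|
| 50% | 64% / 36% | 37% / 63% |
| 70% | 58% / 42% | 56% / 44% |
| 80% | 49% / 51% | 63% / 37% |
| 90% | 34% / 66% | 64% / 36% |

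The loss is measured against a fully efficient analysis and spans 36-66%. At 80% success, intervals are 1/sqrt(0.632) = 1.26 to 1/sqrt(0.490) = 1.43 times as wide.

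**3. Residents versus attendings.** This contrast is between examiners. With ICC rho and m scans each, information kept = [rho + (1-rho)/m] / [rho + (1-rho)/(0.490m)], using the one-sided cut at 80%. For rho = 0.05 and m = 30: 0.0817 / 0.1146 = 0.71, a loss of 29%.

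| ICC | Loss, 30 scans each | Loss, 10 scans each |
|---|---|---|
| 0.05 | 29% | 41% |
| 0.10 | 19% | 33% |
| 0.20 | 11% | 23% |

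Ten scans is an assumed figure for scans with both fluid content and a tube. Within-examiner effects such as scan number stay closer to the per-scan loss.

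**4. Which continuous measure to use.** For a difference in spread, a fully efficient analysis has 2.0 information units per scan. The alternatives have:
- log absolute error: 1 / (pi^2/8) = 0.81
- two-sided success/failure at 80%: 2 x 0.632 = 1.26
- untransformed absolute error: (2/pi) / (1 - 2/pi) = 1.75

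Against untransformed absolute error, the success/failure loss at 80% is therefore 1 - 1.26/1.75 = 28%. Log absolute error does worse than the binary cut here, because errors close to zero dominate it.

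Simulation agrees (independent scans, 400 per group, 80% success in the reference group, two-sided 5% test):
- SD ratio 1.2: power about 65% for log absolute error, 81% for success/failure and 93% for absolute error.
- Bias of 0.2 SD: power about 81% for signed error and 6% for a two-sided success/failure cut.

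**The case against.** **Success may mean content type.** Section 8.1 uses the word that way when describing a cited study ("To achieve a 90% success rate in correctly recognizing gastric content quality in healthy volunteers"), and "Gastric content will be classified into empty, fluid, solid or mixed" is a categorical result. The examination count in section 11.1 ("individual differences in sonography performance can already be detected after 30 to 40 examinations") rests on the same study, whose title concerns qualitative assessment. On that reading no continuous measure is dichotomised. The reading is possible but less well supported: the study's own standard is volume congruence, and the only reference measurement among the collected variables is the suctioned volume. If it were right, section 11.2 would name no model of examiners' volume accuracy, and the same addition would be needed.

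**Binary methods suit the threshold question.** This stands. A success/failure CUSUM fits a critical number of examinations, and the fix keeps it.

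**An extra model is ordinary SAP content.** An addition could be made there. But section 11.2 does name methods for this analysis, so that choice is open to review.

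**Stronger readings the protocol does not support.** A reader might infer that about half the information is lost. That needs a one-sided cut, an 80% success rate and no clustering. The 80% in section 4.2 is a standard to be reached, not an expected success rate, and agreement between two volumes is more naturally a two-sided limit. A reader might also infer that the ml data are abandoned. They are not: the primary endpoint uses them, and section 8.1 commits to analysing the difference.

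**Conclusion.** The point holds as an inexpensive improvement to a secondary analysis; it does not affect the primary endpoint. If success means volume congruence, restricting examiner performance to success/failure discards usable information and leaves over- versus underestimation unexamined.

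The direction is secure on that reading, provided the continuous measure is chosen with care. The size is not fixed by the protocol. It depends on the success rate, the type of limit, the clustering and the number of scans with both fluid content and a tube. The per-scan figures should not be carried over to the resident-attending contrast, where clustering by examiner reduces the loss. The gain is clearest for bias, which a two-sided success limit hardly detects.

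**What to change.** In section 11.2, make the analysis of residents versus attendings and of experience a mixed model with a random examiner effect. Use grade, years of sonographic experience and scan number as predictors. Fit it to:

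- the signed error in ml (calculated minus suctioned), for bias;
- the absolute error in ml, for accuracy, either on its original scale with robust standard errors or through a log-link model for its mean. Do not use log-transformed absolute error.

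Keep logistic regression and CUSUM on success/failure for the competence threshold and the critical number of examinations.

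The cost is protocol or SAP wording and slightly more analysis work. Skewed errors need robust standard errors. No new data are required.
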